**Table 1 Medication List**

Timing	Medication	Procedure
Prior to Procedure	Heparin	Left to the discretion of the interventionist
	Aspirin	100 mg for 3 days prior to procedure or a 300mg prior to procedure.
	Clopidogrel	Loading dose < 6 hours prior or during the procedure of 300- 600 mg Subjects on Clopidogrel therapy (at least 6 days): no loading dose required
	Ticagrelor 	180mg prior to procedure.
During Procedure	Heparin(IV or LMWH)	Per routine hospital practice, it is recommended to maintain an ACT > 250 seconds.

During Procedure	GPIIb/IIIa Inhibitor	Left to the discretion of the interventionist
	Intracoronary Nitroglycerin	100-200 µg post angiography, prior to stent implantation, and post intervention angiograms
Post-Procedure	GPIIb/IIIa Inhibitor	Per routine hospital practice
	Aspirin	100 mg per day
	Clopidogrel 	75 to 150 mg per day Left to the discretion of the interventionist
	Ticagrelor 	90 mg twice per day
Discharge	Aspirin	100 mg per day
	Clopidogrel 	75 to 150 mg per day for a minimum of 12 months.  Dosage left to the discretion of the interventionist
	Ticagrelor 	90 mg twice per day for, a minimum of 12 months.

 Interventionist may substitute to Prasugrel, Ticlopidine or Ticagrelor for subjects who are allergic to Clopidogrel. Subjects on Ticlopidine must have CBC(s) performed per instructions for use.

 Interventionist may choose to use Aspirin together according to the haemorrhage risk other than Clopidogrel.

## 5.5 Interventional Procedure

All implanting interventionists must sign the clinical investigation site signature log and provide a signed and dated CV. All implanting interventionists must also receive adequate CIP training prior to clinical investigation procedure.

Preparation and percutaneous access should be performed according to the standard hospital practice. Both femoral and radial accesses are accepted. The procedure begins once percutaneous access has been made.

### **5.5.1 Baseline Angiography**

Following intracoronary injection of nitroglycerin or isosorbide dinitrate, a baseline angiography of the target vessel must be performed according to the QCA corelab guidelines in at least 2 orthogonal views, presenting the target lesion free of foreshortening or vessel overlap.

### **5.5.2 Randomization**

After in- and exclusion criteria have been checked and written informed consent has been obtained prior to PCI, subjects will be randomized with the eCRF.

- 1/2 Treatment with Orsiro SES
- 1/2 Treatment with Xience Prime™ EES

A randomization may only be done once. If by mistake a subject is randomized twice or more, the first assigned treatment arm will be used.

### **5.5.3 Puncture and Predilatation**

The target lesion should be crossed with a 0.014" guide wire. If predilatation is necessary it is recommended to choose following pre-dilation balloons.

2.0 mm for a 2.25 mm vessel  
2.0 mm for a 2.5 mm vessel  
2.5 mm for a 3.0 mm vessel  
3.0 mm for a 3.5 mm vessel  
3.5 mm for a 4.0 mm vessel

Furthermore, the selected pre-dilatation balloon must be a minimum of two millimeters shorter than the nominal length of the Orsiro stent that is planned to be implanted.

### **5.5.4 Stent Implantation**

Please note that a stent package may not be opened prior to randomization.

The investigator is free to assess the artery diameter and the lesion length either visually or by online QCA during the procedure, always considering the instructions for use. The stent length should cover the target lesion from normal reference vessel proximal to normal reference vessel distal to assure full coverage of the lesion.

Only one clinical investigation stent should be used per lesion. Overlapping is only allowed if the primary stent failed to completely cover the target lesion. In such case the second stent must be the same stent the subject was randomized to, unless clinically contraindicated. Please refer to the IFU of each stent for details of overlapping procedures.

If the stents overlap, the overlapped part must at least be 2mm.

After stent implantation, an angiography must be performed. Following intracoronary injection of nitroglycerin or isosorbide dinitrate, angiograms should be made in the exact same 2 orthogonal views as pre-stenting according to the core lab instructions.

## 5.6 Process before Discharge

Between the end of the procedure and hospital discharge, the following data has to be collected:

- Cardiac biomarkers CK (optional), CK-MB and Troponin I and/or T must be taken within 6-24 hours after procedure.
- Liver function tes (ALT, AST) within 24 hours post-procedure
- Serum creatinine within 24 hours post-procedure
- After the index procedure a 12-lead ECG must be completed within 6-24 hours or at discharge (whichever comes first).

A physical examination will be conducted to verify the anginal status according to CCS or Braunwald classification just prior to discharge. Adverse events and effects, concomitant medications, and any interventional treatment that occurred since the procedure must be recorded before discharge.

**Note:** Every effort must be made to obtain myocardial enzymology values within the specified time ranges. Results of all enzyme target, even measurements performed outside the time range must be documented on the CRFs.

If CK, CKMB and/or Troponin I and/or T elevation is abnormal post-procedure, CK and Troponin measurements should be performed every 8 hours and documented in the eCRF until values have returned to normal.

### 5.6.1 Antiplatelet / Anticoagulation Regimen

For medication please refer to Table 1 under section 5.4

## 5.7 Follow Up Visits

All subjects will be followed through to hospital discharge and will undergo follow-up evaluations at following time points:

### 5.7.1 One Month Clinical Follow Up

All subjects will be contacted for clinical evaluation at 30 days post-procedure ( $\pm$  7 days), including:

- Assessment of the anginal status (CCS or Braunwald),
- Any adverse, or serious adverse events
- Anti-platelet/anti-coagulant treatment plan

### **5.7.2 6 Months Clinical Follow Up**

All subjects will be contacted for clinical evaluation at 180 days post-procedure ( $\pm$  30 days), including:

- Assessment of the anginal status (CCS or Braunwald),
- Any adverse, or serious adverse events
- Anti-platelet/anti-coagulant treatment plan

### **5.7.3 9 Months Clinical Follow Up**

All subjects will return to the clinic for an angiography at 270 days (+ 30 days) post- procedure including:

- Ischemic/anginal status (CCS or Braunwald),
- Any adverse, or serious adverse events/effects
- Anti-platelet/anti-coagulant treatment plan
- Blood routine (total WBC count, platelet count, hemoglobin, hematocrit, and RBC count)
- Liver function test (ALT, AST)
- Serum creatinine
- 12-Lead ECG
- Angiographic assessment of the target lesion

Catheter and imaging position applied by coronary angiogram should be with the same time of stent implanting.

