#### **4.5 Exclusion Criteria**

##### **4.5.1 Clinical Exclusion Criteria**

Subjects will be excluded from the trial if any of the following criteria are met:

- 1) Subject is pregnant and/or breastfeeding or intends to become pregnant during the duration of the study.
- 2) Subject has clinical symptoms and/or ECG changes consistent with acute ST elevation MI (STEMI) within 7 days prior to the index procedure, hemodynamically unstable non-STEMI (NSTEMI) subjects included.
- 3) Subject is hemodynamically unstable.
- 4) Subject is an unacceptable candidate for CABG.
- 5) Subject has a known allergy to contrast medium that cannot be adequately premedicated, or any known allergy to thienopyridine, aspirin, both heparin and bivalirudin, L-605 cobalt-chromium (Co-Cr) alloy or one of its major elements(cobalt, chromium, tungsten and nickel), acrylic, fluoropolymers, silicon carbide, PLLA, sirolimus or everolimus.

- 6) Previous PCI of any target or non-target vessel 9 months prior to the index procedure.
- 7) Planned surgery within 6 months of the index procedure.
- 8) Planned staged treatment during the index procedure or within 30 days after the index procedure.
- 9) History of a stroke or transient ischemic attack (TIA) within 12 months prior to the index procedure.
- 10) Subjects with active bleeding disorders, active coagulopathy, or any other reason, who are ineligible for DAPT.
- 11) Subject will refuse blood transfusions.
- 12) Subject has documented left ventricular ejection fraction (LVEF)  $\leq 40\%$  as evaluated by angiography, echocardiogram, radionuclide ventriculography or any non-invasive imaging method within 90 days prior to the index procedure.
- 13) Subject is dialysis-dependent.
- 14) Subject has impaired renal function (i.e., creatinine  $> 2.0 \text{ mg/dL}$  or  $175 \text{ \mu mol/L}$  determined within 7 days prior to the index procedure).
- 15) Subject has leukopenia (i.e. WBC  $< 3.5 \times 10^9/\text{L}$ ), thrombocytopenia (plt $<100 \times 10^9/\text{L}$ ) or thrombocytosis (PLT $>350 \times 10^9/\text{L}$ ).
- 16) Subject is receiving chronic anticoagulation (e.g. coumadin, dabigatran, apixaban, rivaroxaban or any other agent).
- 17) Subject is receiving oral or intravenous immunosuppressive therapy (inhaled steroids are permitted), or has known life-limiting immunosuppressive or autoimmune disease (e.g., human immunodeficiency virus, systemic lupus erythematosus; diabetes mellitus is permitted).

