## 5.3 Baseline Examinations

Subject clinical investigation eligibility must be confirmed prior to the intervention, through the following tests and examinations:

- Demographics
- For premenopausal women, a pregnancy test must be performed within 72 hours prior to angiography
- Review of in- and exclusion criteria
- Physical examination and relevant medical history including anginal status or myocardial ischemia
- A 12-lead electrocardiogram within 72 hours of the intervention
- Laboratory examination with 7 days of the intervention, including:
  - Infectious diseases screening (hepatitis B surface antigen, hepatitis C antibody, syphilis

antibody (TPPA), and HIV antibody)

- Blood routine (total WBC count, platelet count, hemoglobin, hematocrit, and RBC count)
- Liver function test (ALT、AST)
- Serum creatinine
- Serum glucose
- Serum lipid (triglyceride, cholesterol, high density lipoprotein, low density lipoprotein)
- Cardiac biomarkers CK (optional), CK-MB and Troponin I and/or T

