### **5.7.4 12, 24, 36, 48, 60 Months Clinical Follow Up**

All subjects will be contacted for clinical evaluation at 12, 24, 36, 48, 60 months post-procedure ( $\pm$ 30 days), including:

- Assessment of the anginal status (CCS or Braunwald),
- Any adverse, or serious adverse events
- Anti-platelet/anti-coagulant treatment plan

Table 2: Schedule of treatments and assessments-baseline to 12-month follow up

	Baseline	Procedure	Discharge	30 days ± 7days	180 days ±30 days	270days +30 days	12, 24, 36, 48, 60 months ±30 days
Signed informed consent	X						
Inclusion/Exclusion Criteria	X	X					
Pregnancy Screening	X 						
Medical and Cardiac History	X						
Medication		X 	X 	X 	X 	X 	X 
Blood Routine	X 					X	
Infectious diseases screening	X 						
Serum Creatinine	X 		X 			X	
Liver function test	X 		X 			X	
Serum glucose	X 						
Serum lipid	X 						
CK / CK-MB	X 		X 				
Troponin I or T	X 		X 				
Physical examination and/or Ischemic status	X		X	X	X	X	X
Intervention		X					
Angiography		X 				X 	
12-lead ECG	X 		X 			X	

1. For premenopausal women, a pregnancy test must be performed within 72 hours prior to angiography  
 2. Procedure Medication  
 3. Anti-platelet/anti-coagulant medical therapy  
 4. Within 7 days prior to procedure  
 5. Within 72 hours prior to procedure  
 6. Serum Creatinine within 24 hours post-procedure  
 7. Liver function test(ALT, AST) within 24 hours post-procedure  
 8. CK & CK-MB & Troponin within 6-24 hours post-procedure  
 9. Angiography of all procedure steps and Pre- and Post- procedure in two orthogonal views  
 10. Angiography in the same two orthogonal views as at index procedure  
 11. ECG within 6- 24 hours or before discharge

---

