## **5.8 Unscheduled Coronary Angiogram Follow Up**

Any unplanned angiography and revascularization must be followed by a full clinical evaluation. The required data is to be entered into the eCRF. All films must be sent to the angiographic core laboratory for review.

- If the subject undergoes a clinically driven angiography within 6 months post procedure, having no re-intervention of the target lesion(s), the subject must return for the angiographic follow up visit, 9 months post procedure.
- If the subject undergoes a clinically driven angiography between 6-9 months post procedure, this will be considered as the 9 months follow up angiography.
- If the subject has a re-intervention for in-stent restenosis at any time prior to the 9 months follow up the subject will not have an additional angiography at the 9 months follow up visit.
- However, if the subject has two treated target vessels with the study stent, whereof only one was re-intervened, the subject must return for the repeat angiography at the 9 months follow up visit. If one had revascularization and in-stent restenosis during 6-9 months, the 9 months follow up visit is not needed.

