# **6 CLINICAL INVESTIGATION PLAN DEVIATIONS**

A Clinical Investigational Plan (CIP) deviation is defined as an instance(s) of failure to follow, intentionally or unintentionally, the requirements of the clinical investigation.

All measures must be undertaken to avoid deviations from the CIP. Deviations from the CIP must

---

be documented in the Case Report Form. Original clinical information should be reserved to report the reasons of plan deviations.

Investigators must also adhere to procedures for reporting CIP deviations to their Ethic Committee (EC) in accordance with their specific EC reporting guidelines and procedures. Under emergency circumstances, deviations from the CIP to protect the rights, safety and well-being of human subjects may proceed without prior approval of the sponsor and the EC. Such deviations shall be documented and reported to the sponsor and the EC as soon as possible.

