### 7.2 Subject Study Exit

Investigators should make every effort to ensure subjects complete all protocol-required procedures, including study follow-up visits. However, subjects may be required to exit the study, despite an investigator's best efforts. Good Clinical Practice (GCP) guidelines describe the need for clear subject exit procedures, to include when and how to exit subjects from the study, as well as to outline the type and timing of the follow-up and data collection for these subjects.

Subjects may be exited from this study in the following limited situations:

- Subject death
- Subject withdrawal of informed consent
- Investigator believes it is in the best medical interest of the subject to discontinue study participation due to safety reasons
- Subject is considered a screen failure or a procedure failure

In any of the situations noted above, data collected up to and including the exit of the subject will be used in data analysis. No data will be collected after the exit of the subject from the study. Study exits are expected and will be taken into consideration during data analysis as described. Additionally, subject attrition has been calculated into the study sample size. Therefore, all subjects exited from the study will be counted toward the randomization goal and will not be replaced. Investigators must document, in subject medical records, the reasons and circumstances for all subject exits.

---

In cases where further participation in the study poses potential risk to the subject, study exit should

be considered. In addition to subject safety, consideration should be given to the scientific validity of the primary endpoints when making decisions concerning subject exit. Study follow-up options and requirements for subjects exiting from the study should be determined and applied to all subjects exiting for similar reasons. Deviations in subject eligibility, as defined in the protocol, should be considered protocol violations and reported to the Institutional Review Board (IRB) or Ethics Committee (EC) immediately upon discovery, in accordance with local regulations.

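### No pregnancy test is required before the study-imposed 9-month angiogram, when the only required test is 270 to 303 days old, and section 5.8 does not waive that film for pregnancy

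*Combined protocol and SAP*

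**What the plan says.** All references are to the combined protocol and SAP.

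- **Section 5.3, Baseline Examinations**, opens with the purpose of its tests: "Subject clinical investigation eligibility must be confirmed prior to the intervention". Among them: "For premenopausal women, a pregnancy test must be performed within 72 hours prior to angiography".
- **Table 2** has a Pregnancy Screening row with a single mark, in the Baseline column. Its footnote repeats the rule: "1. For premenopausal women, a pregnancy test must be performed within 72 hours prior to angiography". The 270-day column has marks for blood routine, creatinine, liver function, ECG and angiography, and none for pregnancy screening.
- **Section 5.7.3** sends every subject to the 9-month film: "All subjects will return to the clinic for an angiography at 270 days (+ 30 days) post- procedure including". The list that follows matches the 270-day column of Table 2 and contains no pregnancy test.
- **Section 4.4.1** admits women from age 18, and **section 4.5.1** excludes a woman at entry if "Subject is pregnant and/or breastfeeding or intends to become pregnant during the duration of the study".
- **Section 5.8** gives the cases in which the 9-month film is omitted or replaced. After re-intervention for in-stent restenosis, "the subject will not have an additional angiography at the 9 months follow up visit". A clinically driven angiogram at 6 to 9 months counts as the 9-month film. Pregnancy is not mentioned.
- **Section 12.1** lists the repeat angiogram at 9 months as a risk beyond routine care.

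**The concern.** The sponsor set its own standard for the first angiogram: a premenopausal woman is tested within the preceding three days. The second angiogram also involves radiation and contrast, and it is done for the study, not for her care. Yet the schedule asks for no new test. A site that follows the 270-day column exactly will not perform one, even though it draws blood at that visit.

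The entry exclusion does not fill the gap. It concerns pregnancy and intention at enrolment and cannot detect an unplanned pregnancy months later.

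The second half of the gap is what to do with a positive result. Section 5.7.3 covers all subjects, and the exceptions in 5.8 are all tied to an earlier angiogram or re-intervention. A site that found a pregnancy would have to improvise.

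At stake is an avoidable fetal exposure caused by a study procedure. This is a matter of subject safety, not of inference.

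**Working it through.** The plan gives no figure for this point, so the check is day arithmetic plus an order-of-magnitude count.

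**Age of the latest required test at a scheduled 9-month film**

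Inputs: film on day 270 to day 300 (5.7.3); baseline test 0 to 72 hours, that is 0 to 3 days, before the index angiography (5.3).

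Age = film day + days from test to index angiography.
- Minimum: 270 + 0 = 270 days.
- Maximum: 270 + 30 + 3 = 303 days.
- With the test repeated under the same 72-hour rule: 0 to 3 days.

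**How many women and exposures**

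Inputs from the plan: up to 440 subjects (section 4.2) and 25% loss to follow-up (section 8.1). The plan's inflation reproduces: 162 / 0.75 = 216 per group.

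Inputs assumed here, because the documents do not give them: 2% to 5% of subjects premenopausal; 0.5% to 2% of those unknowingly pregnant on the day of the film.

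- Films expected: 440 × 0.75 = 330, or 165 per arm.
- Women to be tested: 330 × 0.02 = 6.6 to 330 × 0.05 = 16.5, about 7 to 17.
- Expected exposures without a test: 6.6 × 0.005 = 0.033 to 16.5 × 0.02 = 0.33.

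**Effect on the primary endpoint if films are skipped**

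- Share of films forgone, upper end: 0.33 / 330 = 0.1%.
- If one arm lost a whole film: 165 − 1 = 164, against the 162 evaluable subjects per group stated in 8.1.

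Sample size, power and alpha therefore do not change.

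**The case against.** **The footnote may already cover both films.** Footnote 1 of Table 2 refers to angiography without saying which one, while footnotes 4 and 5 refer to the procedure. A site could read it as covering any study angiogram. This is the weaker reading: the footnote hangs on the Baseline mark only, the same sentence stands in 5.3 among the eligibility checks, and 5.7.3 leaves the test out. If both films were meant, the change simply says so.

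**Other safeguards exist.** Exclusion 1 lowers the risk, and sites may test under local practice. Both stand as mitigation. Neither is a protocol requirement for a current test. The consent pages and the Figure 2 flowchart could not be checked, so nothing here rests on the absence of a contraception rule. The fetal items in section 11.3 are a general definition of seriousness and say nothing about the risk in this trial.

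**The event is very rare.** This is true and sets the weight of the point. The counts rest on assumed rates and stay below one expected exposure throughout the range.

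**A site can already deviate for safety.** Section 6 says that "deviations from the CIP to protect the rights, safety and well-being of human subjects may proceed without prior approval", but that sentence is limited to emergency circumstances. A positive test before an elective film does not clearly qualify, so a plain waiver rule is better than reliance on this clause.

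**Conclusion.** The gap holds as a minor subject-safety point. The protocol requires a pregnancy test close to the first angiogram and none before the second, which it imposes itself; the latest required test is then 270 to 303 days old, and 5.8 has no pregnancy waiver. The day count follows from the text alone. The estimate of 0.03 to 0.33 exposures depends on the assumed 2-5% and 0.5-2%.

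A reader might go further and infer that a pregnant subject would have to leave the study at month 9, losing her clinical outcomes to month 60 (60 − 9 = 51 months, five scheduled visits), because section 7.2 says "No data will be collected after the exit of the subject from the study". The documents do not support that:

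- 7.2 confines exit to a short list of situations, and a missed film is not one of them.
- 7.2.1 lets a site record data by phone when a visit cannot be performed. If the subject cannot be reached, a missed visit may be entered instead of an exit.
- For a subject who cannot continue but has not withdrawn consent to further data collection, 7.2 keeps contact on the original follow-up schedule, although it names only vital status as the data to report.
- The 12- to 60-month visits are clinical contacts without radiation, so pregnancy gives no evident safety reason to stop them.

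Nor is there any effect on sample size or the primary analysis beyond a possible missing film.

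**What to change.** 1. In Table 2, add a Pregnancy Screening mark to the 270-day column with the existing 72-hour footnote, and add the same test for premenopausal women to the list in 5.7.3.
2. In 5.7.3 or 5.8, add one sentence: a subject who tests positive does not have the 9-month angiogram and continues scheduled clinical follow-up to 60 months. The waiver in 5.8 for re-intervention is a ready model. This sentence confirms continued follow-up; it does not repair a rule that would end it.

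Cost: about 7 to 17 inexpensive tests under the assumptions above, at a visit that already draws blood; possibly a missing film, with fewer than one expected and the planned 25% loss able to absorb it; and an amendment that, under section 10.6, needs ethics committee approval before use, at up to 15 sites. That administrative step is the main burden.
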